Objectives	
Primary:
 
 • HIV Incidence 
Secondary:
 
 • Number of male partners per participant who obtain an HIV-positive test result • Proportion of unprotected sexual encounters with partners who were HIV-positive or whose HIV status was unknown • Occurrence of intimate partner violence (IPV) • Discussion of HIV testing with partners • Occurrence of couples testing • Qualitative descriptors of how the intervention was used and distributed • Analysis of cost-effectiveness
Number of Subjects	About 2,010 subjects enrolled at IRDO, the field implementing partner in Kenya

CONFIDENTIAL

Main Inclusion and Exclusion Criteria
	
Inclusion Criteria:
 
 • Female • Age \geq 18 years • Currently reside in the study area (hotspot or beach community) • Has resided in study area for at least 6 months in the year prior to enrollment • Intends to stay in the region for at least 24 months • Reports two or more sexual partners within the past 4 weeks • HIV-negative • Ownership or access to a mobile phone • Willing and able to provide informed consent for participant • Not enrolled in another HIV prevention research study 
Exclusion Criteria:
 
 • Does not meet above inclusion criteria • Does not provide informed consent • Does not provide verbal consent to screen for eligibility

Intervention
	
Clusters will be randomized to an intervention group in which women will be given multiple HIV self-tests coupled with referral vouchers for confirmatory testing (for those obtaining an HIV-positive result) over a period of up to 24months or to a comparison group that is given multiple referral vouchers alone for clinic-based HIV testing. The intervention's effect on uptake of HIV testing and identification of HIV-infection among sexual partners of high-risk women, sexual behavior of high-risk women, and HIV incidence among high-risk women will be compared between the two arms.


Statistical Methodology
	
The annual incidence of HIV infection will be compared between study arms through regression modeling using a generalized estimating equations (GEE) approach with a log link and assumed Poisson response distribution (the negative binomial distribution will be used if this distribution is not valid). An offset will be used in this model to account for differential follow-up times. The model will contain a dichotomous covariate for study group; the two-sided ($\alpha = 0.05$) statistical significance of the associated regression coefficient will be assessed with a Wald test performed using robust standard errors. If there are differences in baseline characteristics between the two study groups, a second regression model will be constructed that adjusts for the differing baseline characteristics.

Data and Safety Monitoring Plan
	
Data quality management will be a joint responsibility. The PI, site-PI, and project manager will provide regular oversight of data quality and reporting to all relevant parties. The implementing partner in the field also employs an internal research monitor who will also ensure adherence to study protocols, relevant guidelines, and good clinical practice. A DSMB has been formed to provide regular feedback on data quality and ensure patient safety.

CONFIDENTIAL

Background and Study Rationale

This study will be conducted in full accordance with all applicable University of Pennsylvania Research Policies and Procedures, all applicable US federal and state regulations, all applicable Kenyan federal regulations, as well as in accordance with good clinical practice guidelines.

1 Introduction

This cluster randomized controlled trial will explore whether the provision of multiple oral fluid-based HIV self-test kits to women at higher risk of HIV can be used to promote HIV testing among their sexual partners, facilitate safer sexual decision-making, and ultimately reduce their risk of acquiring HIV. The study will recruit HIV-negative adult women who had two or more sexual partners within the past four weeks in the Nyanza region of Kenya. Beach communities and hotspots where women exchange sex for compensation will be randomized to an intervention group in which women will receive multiple oral fluid-based HIV test kits over a period of up to 24 months, training on how to use the tests, and encouragement to offer tests to their sexual partners. Women in sites that are randomized to the comparison group will be given referral vouchers for clinic-based HIV testing over a period of up to 24-months and encouraged to distribute these vouchers to their sexual partners. The primary outcome will be HIV incidence and secondary outcomes will include self-reported sexual behavior of participants as well as reported diagnoses of HIV-infected persons. Mixed methods research will be utilized to describe the use of self-tests by women and their sexual partners. Cost-effectiveness analyses will also be undertaken.

1.1 Background and Relevant Literature

Widespread HIV testing in sub-Saharan Africa is the essential first step in HIV treatment and prevention efforts. With a number of effective interventions for prevention and treatment of HIV, the global AIDS community is for the first time discussing the possibility of HIV elimination. Although UNAIDS has set out ambitious “90-90-90” goals, most countries in sub-Saharan Africa (SSA) are far from meeting the very first of these targets – that by 2020, 90% of all people living with HIV should know their HIV status [1]. Uptake of HIV testing in SSA remains low, particularly among men [2], and this significantly limits the ability to reduce HIV transmission through safer sexual decision-making and effective treatment as prevention. While community-based testing strategies have had success [3-5], there is an urgent need for creative strategies to increase HIV testing among high-risk populations.

Interventions that can identify HIV-positive persons who are unaware of their status are essential in the high prevalence Nyanza region of Kenya. With an adult HIV prevalence of 15.1% and 450,000 HIV-positive adults and adolescents, data from the Kenya AIDS Indicator Survey (KAIS) suggest that 40% of all persons living with HIV in the country are in the Nyanza region [6]. In the urban and peri-urban sites for the proposed study, HIV prevalence is estimated to be 26% (Homa Bay and Siaya counties, respectively) [7]. While the proportion of adults who have ever tested has risen in the Nyanza region, 50% of those who are HIV-positive remain unaware of their status [7, 8]. The fact that so many HIV-positive individuals remain unaware of their status despite significant expansion of HIV testing services underscores the urgency of finding *creative new testing strategies that can appeal to the unreached population groups*.

Promoting awareness of serostatus is especially important among *high risk populations* such as women who have multiple partners, such as women engaging in transactional sex, as well as their sexual partners. The vulnerability to HIV of women who engage in transactional sex has been extensively documented [9]. Female sex workers (FSW) in SSA have HIV prevalence that often exceeds 50% and is 10-20 times higher than prevalence in the general population [10, 11]. HIV prevalence among FSW in the proposed study setting is estimated to be 56.5% [12] and recent data indicate there are 534 active FSW “hotspots” of commercial sex work, with an estimated 4,041 FSW [13]. Fisher folk communities (FFC) – also referred to as beach communities – similarly have a higher burden of HIV-1 infection than respective general populations [14-16]. Studies have reported HIV prevalence between 25–29% and annual incidence rates of 3.39-4.9% in Kenyan and Ugandan FFC. These figures are 3–4 times higher than respective national averages. Unlike general populations, fishing communities tend to be socially marginalized and often stigmatized. Due to ready cash from fishing activities coupled with staying away from their spouses and other family, FFC are characterized by a high presence of bars, lodges and

CONFIDENTIAL

entertainment halls, transactional sex (sex for money and sex for fish), high alcohol consumption and multiple sexual partnerships, but very limited access to health services.

Oral fluid-based HIV self-testing is a promising biomedical technology that has the potential to overcome many of the barriers to HIV testing. With self-testing, individuals collect their own sample and perform a simple, rapid HIV antibody test in the absence of a provider. It offers increased convenience, privacy, and autonomy, and has the potential to normalize regular testing. Existing research shows a high level of acceptability and demand for self-testing across a wide range of populations and settings, as well as good accuracy in the hands of lay users [17-27]. Participants in these studies – including studies we have conducted in Kenya – report that self-testing would reduce stigma around HIV testing, a formidable barrier, as well as increase convenience and confidentiality. Interest is typically highest among high-risk groups and those who have never tested for HIV [24]. Regulated self-testing has been included in Kenya’s national HIV testing guidelines since 2009 [28, 29] and a growing number of countries – including Kenya – are considering scaling-up self-testing [27]. Yet there is little evidence on how best to deploy self-tests so as to ensure that testing is increased among high-risk individuals *not reached* by other HIV testing modalities.

A promising but under-explored approach is the provision of *multiple* self-tests to individuals who are then encouraged to distribute the tests to others in their sexual networks (i.e. ‘secondary distribution’). The use of networks to reach high-risk persons has proven to be successful in several areas of public health [30, 31]. Given the need for regular repeat testing among women with multiple partners (including those engaged in transactional sex and women in beach communities) as well as their sexual partners, we have shown in a recently completed pilot study in Kisumu that an especially promising strategy is to provide women with multiple self-tests that they can then use to initiate partner testing or couples testing [22]. This strategy has the potential to generate multiple HIV prevention benefits, including promotion of male partner testing and facilitation of safer sexual behaviors.

Studies that we and others have conducted suggest that an important HIV prevention benefit of self-tests may stem from their potential use as a “point-of-sex” testing technology. Point-of-sex testing, particularly when a condom would not otherwise be used, may promote safer sexual decision-making, thereby functioning as an HIV prevention intervention. Secondary distribution of self-tests has been undertaken among men who have sex with men (MSM) in New York City [21, 32, 33]. Results from the studies with MSM have been encouraging – demonstrating that MSM used self-tests to screen potential sexual partners for HIV and decide whether to use condoms (or even avoid sex altogether) when partners declined to test or when an HIV-positive result was obtained. Our pilot study with FSW in Kenya obtained similar results, and it was the first study to explore the feasibility of secondary distribution of self-tests in SSA [22, 34]. Another randomized controlled trial we recently completed among pregnant and postpartum women in Kisumu also demonstrated the feasibility of this intervention [35]. Rigorous evaluation of such a strategy among high-risk women, with measurement of HIV incidence and sexual risk behaviors, is a natural next step.

Women with multiple partners are an important population in which to evaluate secondary distribution of self-tests. Since male partners of these women are more likely to be HIV-positive than other men and are less likely to know their HIV status, this strategy could be an efficient way to identify HIV-positive persons (furthering the first of the 90-90-90 goals). Moreover, it could facilitate safer sexual decision making by women and thereby reduce their risk of HIV acquisition. Studies that we and others have conducted show suboptimal levels of condom use by FSW with their sexual partners [12, 36, 37]. *If women are able to use self-tests to identify partners who are HIV-positive and make safer sexual decisions, as our preliminary data suggest, it could have a transformative impact as an HIV prevention strategy.* As such, the National AIDS and STI Control Programme (NASCOP) in Kenya and the Ministry of Health (MOH) in Siaya have expressed strong support for evaluating such an intervention.

CONFIDENTIAL

2 Study Aims

2.1 Primary Aim

- *Aim 1.* To determine the effect of distributing multiple HIV self-tests (HIVST) on uptake of HIV testing, identification of HIV-infection among sexual partners of high-risk women, changes in sexual behavior of high-risk women, and HIV incidence among high-risk women.

2.2 Secondary Aims

- *Aim 2.* Use a mixed methods approach to identify and address safety concerns and general perceptions regarding use and distribution of the intervention by high risk women and their sexual partners
- *Aim 3.* Assess cost-effectiveness of the intervention and obtain information necessary to inform scale-up of the intervention in Kenya and other countries

3 Investigational Plan

3.1 General Design

We will conduct a cluster randomized trial among HIV-negative women in the Nyanza region of Kenya. Clusters will be defined as hotspots where women exchange sex and FFCs along beaches in the study region. Clusters will be randomized to an intervention group in which women will be given *multiple* HIV self-tests coupled with referral vouchers for confirmatory testing (for those obtaining an HIV-positive result) or to a comparison group that is given multiple referral vouchers alone for clinic-based HIV testing. We will test for HIV and collect survey information, including sexual behaviors and HIVST use, from women at a baseline visit and every six months for up to 24 months.

3.2 Allocation to Interventional Group

Clusters of geographic areas will be matched on the basis of population and type (hotspot for women who exchange sex or beach community) and then randomized to two study groups (receiving HIV self-test kits or referral cards for HTS based testing) in a 1:1 ratio. Computer-generated randomization will be used to determine group assignment of clusters. There will be no blinding associated with the study.

3.3 Study Measures

An original questionnaire was developed for to assess various participant characteristics at baseline. This questionnaire includes questions about participant's socio-economic characteristics, sexual behavior, HIV testing history as well as the PHQ-9 mental health scale and a gender-based violence assessment. Follow-up data will be obtained through short surveys as well as a follow-up questionnaire administered at approximately 6-month intervals.

3.4 Study Endpoints

3.4.1 Primary Study Endpoint

In keeping with the intervention's potential to general multiple HIV prevention benefits, we will assess a primary outcome of HIV incidence and two secondary outcomes (one pertaining to HIV testing and the other to sexual behavior).

HIV incidence. All participants will be asked to come for HIV testing at baseline/screening and every 6 months during the follow-up period. We will use these data to measure HIV incidence among participants over a maximum of 24-month period. To limit attrition and obtain follow-up information, at 6-month intervals, participants will be offered compensation for transportation and time they take to undergo HIV testing and completing the follow-up surveys mentioned above. Our hypothesis is that the intervention

group will have lower HIV incidence than the comparison group. Obtaining a measure of HIV incidence among participants will also be useful for performing cost-effectiveness analyses in Aim 3.

3.4.2 Secondary Study Endpoints

Number of male partners per participant who obtain an HIV-positive test result. This information will be obtained directly from the index participants. For each participant, we will assess the number of reported partners who tested for HIV and obtained a reactive result. We hypothesize that the number of HIV-positive male partners identified per participant will be higher in the intervention group than the comparison group.

Proportion of unprotected sexual encounters with partners who were HIV-positive or whose HIV status was unknown. This outcome will be based on data from follow-up surveys and will assess the HIV risk that participants were exposed to during the follow-up period. We expect, based on pilot data, that women in the intervention group will be able to utilize self-tests to facilitate HIV results disclosure with sexual partners and make safer sexual decisions. Thus, we hypothesize that the intervention group will be less likely than the comparison group to have unprotected sex with a partner of unknown or HIV-infected status.

Additional Outcomes. Other outcomes that we assess will include the occurrence of intimate partner violence (IPV), discussion of HIV testing with partners, and occurrence of couples testing. The outcomes of Aim 2 will be a qualitative narrative of how HIVST are perceived and used. Aim 3 will use the primary outcome to determine the cost-effectiveness of HIVST distribution in this setting.

4 Study Population and Duration of Participation

The study will include women who report having two or more partners in the past month, including women who exchange sex and high-risk women residing in beach communities. In each of the selected clusters (hotspots or beach communities), we will sample women and assess their eligibility. We will also interview male partners of women who participate in the study, to collect data on their experience. Women enrolled in the main study will be followed for up to two years. Male partners who are contacted will participate in one qualitative interview.

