Participants in clusters randomized to the intervention group will be provided with multiple self-tests over a period of up to 24 months and encouraged to distribute the tests to individuals in their sexual networks with whom they may have unprotected sex. Participants will be given several HIV self-tests *initially* and informed that they can obtain *additional* self-tests during the intervention period. Each self-test will include clear instructions for use, a list of HIV testing services (HTS) clinics where those obtaining reactive self-tests can seek confirmatory testing (as is recommended by Kenya's testing guidelines). In order to encourage individuals who obtain a reactive self-test to seek confirmatory testing *and* to measure uptake

CONFIDENTIAL

of confirmatory testing, a *VCT referral voucher* will be included with each self-test. Each self-test will also include a study phone number that participants or male partners of participants may call to obtain information about how to use the test and receive information on follow-up services.

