At enrollment, participants will be trained on how to use HIV self-tests using methods and materials developed in our pilot study. They will be counseled on how to discuss HIV self-testing with sexual partners and on the importance of using their own discretion and assessing the risk of IPV when deciding whether to offer a self-test to a sexual partner. The concept of the HIV “window period” and the importance of condom use and other sexual risk reduction strategies will also be discussed. As part of the pilot study we carried out last year, we developed talking points for study staff to use when enrolling participants and giving them multiple self-tests. These talking points, as well as lessons we learned in the pilot study, will be fully incorporated into the education and counseling that participants will receive during enrollment. Participants will be reminded to use condoms whenever possible and reserve self-tests for primary partners as well as current and potential partners with whom unprotected sex is likely. The counseling message outlined in the study procedures discusses the rate of false negative results (up to 8%) that can occur when using the kits and gives possible reasons for false negatives to occur, including: improper use of the test, antibodies cannot be detected because of the window period, or the HIV positive person is on ARVs and virally suppressed. False positives are also explained such that any “reactive” test does not mean HIV positive and that any reactive test should be confirmed at a local VCT clinic for a proper medical diagnosis.

We will use the FDA-approved OraquickAdvance Rapid HIV-1/2 Antibody Test, which achieved 92% sensitivity in premarket self-testing in the US [44]. This oral fluid-based test detects antibodies to HIV-1 and HIV-2 in 20 minutes. Currently, the Oraquick self-test is approved for use in Kenya and the government is considering its broader use throughout the country. In our prior study, we developed easy-to-follow instruction materials on how to use the self-test. These instruction materials will be included with each self-test that is distributed to study participants.

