5.2 Follow-Up Visits

5.2.1 Monthly Distribution Visits

Each month, research assistants will schedule a time to visit each cluster where enrollments have taken place. Participants will be made aware of the venue and times that the research assistant will be available, and they can attend the event to replenish their stock of either HIVST kits or HTS referral cards. Fingerprints are collected to verify the participant's identity and a record is kept of the serial number of the HIVST kits or referral cards. Participants will be asked how they used and distributed to cards to help guide additional discussion about the number of HIVST kits or VCT referral cards to receive and if relevant counseling messages need to be reiterated. The research assistants will also use this time to answer any questions about the study, intervention use, distribution, or adverse event reporting that the participants would like to discuss. Participation in the monthly distribution visits is optional; if participants do not need to replenish their supply, have no questions, or cannot attend, there is no additional follow-up for these visits. These visits will take approximately 10 minutes, on average.

5.2.2 6-Monthly Follow-Up (Months 6, 12, 18, and 24)

The 6-monthly follow-up procedures will be used to test for HIV, collect information about the use of the interventions, and address any questions the participant may have. These visits will take approximately 45 minutes. Specific procedures include:

- Fingerprint verification of participant's identity
- HIV rapid test is performed according to Kenyan HTS guidelines.
- Administration of the follow-up visit questionnaire
- Distribution of the HIV self-test kits or HTS referral cards, to include "refresher" counseling session on how to safely use and distribute the intervention.
- Reimburse participant for travel and time

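### The partner-diagnosis outcome counts only reactive results that the woman knows and reports, and self-test results are likely to be more visible to her than clinic results, so part of any difference may be ascertainment

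*Combined protocol and SAP*

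**What the plan says.** Section 3.4.2 names the outcome as the number of male partners per participant who obtain an HIV-positive result, and hypothesises that more such men will be identified in the intervention group. On the source it says "This information will be obtained directly from the index participants", and on the count, "we will assess the number of reported partners who tested for HIV and obtained a reactive result".

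The arms differ in how partners test:

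- **Intervention.** Women hand out oral-fluid kits. Section 5 says "This oral fluid-based test detects antibodies to HIV-1 and HIV-2 in 20 minutes". Section 1.1 presents the kits as a technology for use at the moment of sex: "Point-of-sex testing, particularly when a condom would not otherwise be used, may promote safer sexual decision-making".
- **Comparison.** Section 3.1 describes a "comparison group that is given multiple referral vouchers alone for clinic-based HIV testing".

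Under the second secondary outcome (unprotected encounters), section 3.4.2 expects that "women in the intervention group will be able to utilize self-tests to facilitate HIV results disclosure with sexual partners".

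The trial is unblinded (section 3.2). Section 6.2.2 analyses the count with the same GEE model as the primary outcome, with an offset for number of partners if possible. It describes no verification of partner results and no sensitivity analysis for how results become known.

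**The concern.** The name and hypothesis concern men who are diagnosed. The measurement concerns men whose positive result reaches the woman. These agree across arms only if a positive result is equally likely to reach her, and be reported, after a self-test and after a clinic visit. The protocol's own expectation is that self-tests help results to be disclosed. If so, the intervention raises the count partly by making results more visible, even when equal numbers of men test positive. An offset for number of partners adjusts for how many men could test, not for how many results she learns.

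At stake is the interpretation of the first of two named secondary outcomes: a higher count could be reported as more men diagnosed when part or all of it is better knowledge of results.

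**Working it through.** **The plan's own figures.** The documents give no rate, power or disclosure probability for this outcome, so there is nothing to reproduce for it directly. The illustration below borrows the primary-outcome design (section 6.1), so that was checked first. With rates of 0.045 and 0.0225 per year, coefficient of variation k = 0.40 and 30 × 0.9 × 1.5 = 40.5 person-years per cluster, the usual formula for unmatched clusters gives

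c = 1 + (1.960 + 0.842)² × [(0.045 + 0.0225)/40.5 + 0.40² × (0.045² + 0.0225²)] / 0.0225² = 33.12 clusters per arm,

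or 1,987 women against the stated 1,980. The design reproduces. It has no bearing on the concern beyond supplying 33 clusters of 27 retained women per arm.

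**The bias.** Let μ1 and μ0 be the true mean numbers of positive partners per woman, and a1 and a0 the probabilities that she knows and reports a positive result in the self-test and voucher arms. Leaving false reports aside,

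reported ratio = (μ1 × a1)/(μ0 × a0) = true ratio × (a1/a0).

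With a true ratio of 1, the reported ratio is a1/a0. The assumed range runs from 0.9/0.9 = 1.0 to 1.0/0.5 = 2.0.

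**Effect on the test.** With a common true mean μ, the approximate variance of the log ratio is

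v = [1/(27 × μ × a1) + k²]/33 + [1/(27 × μ × a0) + k²]/33.

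Example: for μ = 0.10, a1 = 0.9, a0 = 0.7 and k = 0.40, v = (0.412 + 0.16)/33 + (0.529 + 0.16)/33 = 0.0382, so SE = 0.195. Then ln(0.9/0.7) = 0.251, z = 1.29, and the chance of exceeding 1.96 is 25%.

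Chance of a significant result favouring the intervention when the true ratio is 1:

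| a1/a0 | Reported ratio | μ = 0.05 | μ = 0.10 | μ = 0.20 |
|---|---|---|---|---|
| 0.9/0.9 | 1.00 | 2.5% | 2.5% | 2.5% |
| 0.9/0.8 | 1.125 | 6.8% | 9.0% | 11.9% |
| 0.9/0.7 | 1.29 | 16.2% | 25.0% | 36.8% |
| 0.9/0.6 | 1.50 | 32.7% | 51.8% | 72.2% |
| 0.9/0.5 | 1.80 | 54.9% | 79.5% | 94.6% |

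The values of a1, a0 and μ, and the use of k = 0.40 for this outcome, are all assumptions. If disclosure were higher after clinic testing the bias would reverse: 0.5/0.7 gives 0.71.

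**Which bounds work.** Suppose 1,000 men test per arm and 100 are positive in each. All self-test results reach the woman; clinic results reach her for 50% of positives and 90% of negatives (all assumed). Control then shows 50 known positives among 50 + 810 = 860 known results, with 140 unknown.

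- Unknowns all negative: 100/50 = 2.0.
- Unknowns positive at the known rate: 140 × 50/860 = 8.1, so 100/58.1 = 1.72.
- Unknowns all positive: 100/(50 + 140) = 0.53.

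The true ratio of 1.0 lies outside 1.72 to 2.0 but inside 0.53 to 2.0. Imputing at the known rate fails because it assumes that disclosure does not depend on the result.

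**The case against.** The strongest reply is that neither direction nor size is established. A man may take a kit away and test alone: section 5 packs instructions and a telephone number that partners can use with every kit. A couple may attend a clinic together, and couples testing is itself an outcome to be measured. A reader might infer that a self-test result is seen directly while a clinic result must be told. The documents do not support so sharp a contrast, and the assumed range begins at no bias. This stands: the gap is one of degree.

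The survey may also already separate partners of unknown status, since the second secondary outcome needs that category, and section 5 asks about partners who do and do not accept kits or vouchers. The questionnaires are attachments not available here. This stands as a reason to check the form before changing it.

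A reader might further infer that voucher records offer an unbiased count, because at monthly visits "a record is kept of the serial number of the HIVST kits or referral cards" and each kit carries a voucher to encourage "individuals who obtain a reactive self-test to seek confirmatory testing" and measure uptake of that testing. That goes too far. The serials are recorded at hand-out to women. No section describes clinics returning vouchers, serials or results, and apart from about 30 interviewees the men are not enrolled. The voucher also means different things by arm: a first test in control, a second and confirmatory test in the intervention. Men who react on a self-test and skip confirmation would be lost from the intervention count only.

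None of this removes the core point. The sole source is the woman, the route by which results reach her differs by arm, and the plan has no analysis for it.

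**Conclusion.** The concern holds as a limit on interpretation. As planned, this outcome measures reactive partner results known to and reported by the woman, and a difference cannot by itself be read as more men diagnosed. Inflation is 1.0- to 2.0-fold under assumed probabilities of 0.9/0.9 to 1.0/0.5. The likely direction favours the intervention, on the strength of the protocol's own expectation about disclosure, but it is not certain.

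A reader might infer that the trial's main result or its cost-effectiveness analysis is compromised. The documents do not support that. HIV incidence is measured by study testing of the women and is unaffected. Section 3.4.2 says that Aim 3 uses the primary outcome. Section 6.2.2 adds increased identification of HIV-positive men without naming the source of that input, and plans extensive sensitivity analyses. Aim 3 is affected only if that input comes from this measure.

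**What to change.** 1. Relabel the outcome and its hypothesis as *partners with a reactive result as known to and reported by the woman*, and state that it will not be interpreted alone as more men diagnosed.
2. From the follow-up survey, tabulate by arm the partners who tested with result unknown to the woman. Add that response option if the form lacks it.
3. Add a sensitivity analysis that divides the reported ratio and its confidence limits by a1/a0 over a stated range, including values below 1. Report the value at which the effect disappears: for the point estimate this is the reported ratio itself, and for significance it is the lower confidence limit.
4. Give extreme bounds that treat unknown results as all negative and as all positive in each arm separately, so that the limits pair all negative in one arm with all positive in the other. Do not impute at the arm's known rate. Men who conceal that they tested never enter the unknown category, so the a1/a0 analysis is needed as well as the bounds.
5. If returned vouchers are in fact collected, report them by arm as descriptive only, noting that they may under-count the intervention arm.
6. State whether the Aim 3 input for identified men comes from this measure.

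The cost is a few lines of SAP text, possibly one survey response option, and a wider or less favourable statement of this secondary result.
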